11.6.2.2. Handling of Missing/Partial Dates

Element	Reporting Detail
---------	------------------

Element	Reporting Detail				
General	Partial dates will be displayed as captured in subject listing displays.				
Concomitant Medication	Partial start dates of prior and concomitant medications will be assumed to be the earliest possible date consistent with the partial date. In the case of a missing year, the year will be assumed to be the year part of informed consent date of that subject. In the case of a completely missing start date, the start date will be assumed to be prior to date of the first administration of study medication. Partial stop dates of prior and concomitant medications will be assumed to be the latest possible date consistent with the partial date. In the case of a completely missing stop date, the medication will be assumed to be ongoing.				
Time to Delivery	
For the delivery date/time of the primary endpoint,
 
 Missing data with respect to time to delivery endpoint is unlikely to occur. If it occurs and the dates are missing, the last assessment date of a mother prior to delivery phase will be used. If the times are missing, a "00:00" will be used for the time. 				
Adverse Events (General)	
 If the dates are missing for on-treatment, or post-treatment AEs, imputation of AE dates may be performed if needed. The eCRF allows for the possibility of partial dates (i.e., only month and year) to be recorded for AE start and end dates; that is, the day of the month may be missing. Start or end dates which are completely missing (i.e. no year specified) will remain missing, with no imputation applied. There will be no imputation for AE data listings 				
Adverse Events (Mother)	
 Any partial dates for adverse events will be flagged to data management. If the full date cannot be ascertained, the following assumptions will be made whether the AE occurred on-treatment or post-treatment : 
 
 Start Date	 
 If the partial date is a start date, a '01' will be used for the day and 'Jan' will be used for the month. 
 For AEs which can occur only during or after labor/delivery (ex. postpartum hemorrhage), if these results in a date are prior to the delivery date, then the delivery date will be assumed to be the start date. Applicable AEs will be identified by PPD/GSK medical monitor. For other AEs that occur prior to labor or delivery, if these results in a date are prior to the first study treatment date, then the first study treatment date will be assumed to be the start date. The AE will then be considered to start on-treatment (worst case). 	
 
 End Date	 
 If the partial date is a stop date, a '28/29/30/31' will be used for the day (dependent on the month and year) and 'Dec' will be used for the month. 	
 
	Start Date	
 If the partial date is a start date, a '01' will be used for the day and 'Jan' will be used for the month. 
 For AEs which can occur only during or after labor/delivery (ex. postpartum hemorrhage), if these results in a date are prior to the delivery date, then the delivery date will be assumed to be the start date. Applicable AEs will be identified by PPD/GSK medical monitor. For other AEs that occur prior to labor or delivery, if these results in a date are prior to the first study treatment date, then the first study treatment date will be assumed to be the start date. The AE will then be considered to start on-treatment (worst case). 	End Date	
 If the partial date is a stop date, a '28/29/30/31' will be used for the day (dependent on the month and year) and 'Dec' will be used for the month.
Start Date	
 If the partial date is a start date, a '01' will be used for the day and 'Jan' will be used for the month. 
 For AEs which can occur only during or after labor/delivery (ex. postpartum hemorrhage), if these results in a date are prior to the delivery date, then the delivery date will be assumed to be the start date. Applicable AEs will be identified by PPD/GSK medical monitor. For other AEs that occur prior to labor or delivery, if these results in a date are prior to the first study treatment date, then the first study treatment date will be assumed to be the start date. The AE will then be considered to start on-treatment (worst case). 				
End Date	
 If the partial date is a stop date, a '28/29/30/31' will be used for the day (dependent on the month and year) and 'Dec' will be used for the month. 				

Element	Reporting Detail					
		
 ○ For AEs which can occur only during the pregnancy (ex. gestational diabetes), if these results in a date are after the delivery date, then the delivery date will be assumed to be the end date. Applicable AEs will be identified by PPD/GSK medical monitor. ○ For other AEs that occur only during or after labor/delivery, if these results in a date are after the last assessment date or contact date, then the last assessment date or contact date will be assumed to be the end date. 				
Adverse Events (Neonate)	
 • Any partial dates for adverse events will be flagged to data management. If the full date cannot be ascertained, the following assumptions will be made: 	
 
 Start Date	 
 • If the partial date is a start date, a '01' will be used for the day and 'Jan' will be used for the month. • However, if these results in a date are prior to the birth date, then the birth date will be assumed to be the start date. • The AE will then be considered to start on-treatment (worst case). 	
 
	Start Date	
 • If the partial date is a start date, a '01' will be used for the day and 'Jan' will be used for the month. • However, if these results in a date are prior to the birth date, then the birth date will be assumed to be the start date. • The AE will then be considered to start on-treatment (worst case). 		
Start Date	
 • If the partial date is a start date, a '01' will be used for the day and 'Jan' will be used for the month. • However, if these results in a date are prior to the birth date, then the birth date will be assumed to be the start date. • The AE will then be considered to start on-treatment (worst case). 					
	End Date	
 • If the partial date is a stop date, a '28/29/30/31' will be used for the day (dependent on the month and year) and 'Dec' will be used for the month. • If these results in a date are after neonatal death date, then neonatal death date will be assumed to be the end date. • If the dates are after the last assessment date or contact date, then the last assessment date in medical record or contact date will be assumed to be the end date. • However, if these results in a date are more than 28 days after EDD, then 28 days after EDD will be assumed to be the end date. 				
Adverse Events (Fetus)	
 • Any partial dates for adverse events will be flagged to data management. If the full date cannot be ascertained, the following assumptions will be made: 	
 
 Start Date	 
 • If the partial date is a start date, a '01' will be used for the day and 'Jan' will be used for the month. • However, if these results in a date are prior to the first study treatment date, then the first study treatment date will be assumed to be the start date. • The AE will then be considered to start on-treatment (worst case). 	
 
 End Date	 
 • If the partial date is a stop date, a '28/29/30/31' will be used for the day (dependent on the month and year) and 'Dec' 	
 
	Start Date	
 • If the partial date is a start date, a '01' will be used for the day and 'Jan' will be used for the month. • However, if these results in a date are prior to the first study treatment date, then the first study treatment date will be assumed to be the start date. • The AE will then be considered to start on-treatment (worst case). 	End Date	
 • If the partial date is a stop date, a '28/29/30/31' will be used for the day (dependent on the month and year) and 'Dec'
Start Date	
 • If the partial date is a start date, a '01' will be used for the day and 'Jan' will be used for the month. • However, if these results in a date are prior to the first study treatment date, then the first study treatment date will be assumed to be the start date. • The AE will then be considered to start on-treatment (worst case). 					
End Date	
 • If the partial date is a stop date, a '28/29/30/31' will be used for the day (dependent on the month and year) and 'Dec' 					

Element	Reporting Detail
	
will be used for the month.
 
• However, if these results in a date are after the birth date or fetal death date, then the birth date or fetal death date will be assumed to be the end date.

11.7. Appendix 7: Primary and Sensitivity Analyses for Primary and Key Secondary Endpoints with Missing Data

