6.3.8. Time Period and Frequency of Detecting AEs and SAEs

The investigator or site staff is responsible for detecting, documenting, and reporting events that meet the definition of an AE or SAE.

Adverse events and SAEs will be collected from the start of study treatment and until the follow-up contact (see Section [6.3.10](#)) at the time points specified in [Table 5](#).

Medical occurrences that begin prior to the start of study treatment but after obtaining informed consent may be recorded on the Medical History/Current Medical Conditions section of the eCRF. Additionally, if a condition with a start date predating Day 0 (Screening) is subsequently discovered, the condition should be recorded in the Medical History eCRF.

Any SAEs assessed **as related** to study participation (e.g., protocol-mandated procedures, invasive tests, or change in existing therapy) or related to a GSK product will be recorded from the time a subject consents to participate in the study up to and including any follow-up contact.

All SAEs will be recorded and reported to GSK/PPD within 24 hours, as indicated in Section [6.3.11](#).

Investigators are not obligated to actively seek AEs or SAEs in former study subjects. However, if the investigator learns of any SAE, including a death, at any time after a subject has been discharged from the study, and he/she considers the event reasonably related to the study treatment or study participation, the investigator must promptly notify GSK/PPD.

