8.2.3. Adverse Events

AEs will be coded using the Medical Dictionary for Regulatory Activities (MedDRA) coding dictionary. A mapping of the MedDRA primary system organ class (SOC) and preferred term (PT) that each verbatim term has been coded to will be provided in a listing. In general, AEs will be presented in descending order from the SOC with the highest total incidence (that is, summed across all treatment groups) for any adverse event within the class to the SOC with the lowest total incidence. Within the SOC level, AEs will be presented in descending order from the PT with the highest total incidence to the PT with the lowest total incidence. If the total incidence for any two or more PTs within an SOC is equal, the PTs will be presented in alphabetical order. A PT will not be

presented if no adverse events occur within the level. At each level of summarization, a subject is counted only once if the subject reported one or more events.

The number and percentage of subjects with any AE started on or after the first study treatment will be summarized by treatment group in the tables. All AEs will be listed.

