8.2.3.2. Adverse Events by Maximum Grade or Intensity

A summary of AEs by grade or intensity will be presented in a table. The grade or intensity that will be presented represents the most extreme grade or intensity captured on the CRF page. The possible grades or intensities are “Not applicable”, “Mild or Grade 1”, “Moderate or Grade 2”, “Severe or Grade 3” and “Grade 4”. In the grade or intensity table, if a patient reported multiple occurrences of the same AE, only the most severe will be presented. AEs that are missing grade or intensity will be presented in tables as “Grade 4” but will be presented in the data listing with a missing grade or intensity.

The AE will be summarized by maternal, fetal and neonatal events, separately.

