8.2.3.4. Serious Adverse Events

The seriousness of an AE should be assessed by the Investigator independently from the severity of the AE. A serious AE (SAE) is defined as any untoward medical occurrence that at any dose results in death, is life-threatening, requires hospitalization or prolongation of existing hospitalization, results in disability/incapacity, is a congenital anomaly/birth defect, or is possible of drug-induced liver injury with hyperbilirubinemia.

Important medical events that may not result in death, be life-threatening, or require hospitalization may be considered SAEs when, based upon medical judgment, they may jeopardize the subject and may require medical or surgical intervention to prevent one of the outcomes listed above.

SAEs will be reported in the similar manner as all AEs. A listing of SAEs will be provided. Also, the above summary will be produced by subgroups as defined in Section **Error! Reference source not found.**

The SAEs will be summarized by maternal, fetal and neonatal events, separately. Also, the maternal SAEs by treatment phase (on-treatment, post-treatment) defined in Section 11.3.3 will be summarized.

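### Adverse events with no start date at all have no defined route into the safety tables, and two rules in the same SAP cell conflict on how to handle them.

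*SAP*

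**What the plan says.** The general AE row of SAP 11.6.2.2 contains two statements that bear on this point. One is permissive: "If the dates are missing for on-treatment, or post-treatment AEs, imputation of AE dates may be performed if needed". The other is firm and applies to dates lacking even a year: "Start or end dates which are completely missing (i.e. no year specified) will remain missing, with no imputation applied".

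SAP 8.2.3 sets the criterion for the tables: "The number and percentage of subjects with any AE started on or after the first study treatment will be summarized by treatment group". It adds that "All AEs will be listed". The criterion carries over to other displays: SAP 8.2.3.4 states "SAEs will be reported in the similar manner as all AEs", and 8.2.3.6 and 8.2.3.7 say much the same for AEs of special interest (AESIs) and disease-related events (DREs).

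SAP 11.3.3 defines pre-, on- and post-treatment AEs by comparing the AE start date with the treatment dates. It has a note for a missing treatment stop date and none for a missing AE start date.

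On collection, Protocol 6.3.8 says "Adverse events and SAEs will be collected from the start of study treatment". The same section records SAEs related to study participation or to a sponsor product from consent.

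**The concern.** The table criterion and the treatment states both need a start date, and the SAP declines to supply one when it is wholly missing. An event can therefore be known, recorded and listed, yet have no stated place in a summary table.

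This also runs against the SAP's own habits. For intensity, 8.2.3.2 says "AEs that are missing grade or intensity will be presented in tables as" Grade 4, the highest category. A missing causality answer counts as drug-related in 11.3.3. A partial AE start date that would fall too early is moved up to first treatment or, for a neonate, to birth, and the SAP calls this the worst case. Even concomitant medications, in the same table of date rules, get a default for a start date that is completely absent. Undated AEs are the exception.

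At stake is an undercount of safety events, and it would fall on the worst-documented ones.

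**Working it through.** The plan gives no figure to reproduce. The check applies its rules literally and then works out what one subject weighs.

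**Step 1: follow four kinds of start date through the maternal rules.** Take an illustrative first treatment date of 10 June 2016 and an AE not confined to labor or delivery. The inputs are the imputation rules in SAP 11.6.2.2 and the criterion in 8.2.3.

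| Start date as recorded | After SAP 11.6.2.2 | Meets the 8.2.3 criterion? |
|---|---|---|
| 11 June 2016 | 11 June 2016 | Yes |
| June 2016 | 1 June, moved up to 10 June 2016 | Yes |
| 2016 only | 1 January, moved up to 10 June 2016 | Yes |
| Nothing recorded | Still missing | Cannot be evaluated |

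Losing the day, or the day and month, leaves the event in the table as on-treatment. Losing the year as well leaves it unclassified.

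**Step 2: does the permissive bullet settle it?** It covers AEs already known to be on- or post-treatment. Under 11.3.3 that status comes from the start date, which is the item missing. The bullet names no value and no trigger, and the firm bullet in the same cell says the opposite.

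**Step 3: how likely is an undated AE to be post-dose?**
- *Mothers and fetuses: very likely, not certain.* Protocol 6.3.8 starts general AE collection at first treatment and lets events between consent and dosing be recorded as medical history. But related SAEs run from consent, Protocol 3.1.1 begins AE monitoring at Screening, and SAP 11.3.3 has a pre-treatment state.
- *Neonates: always.* The Neonatal Safety population (SAP 4) is infants of treated mothers, and birth follows the start of infusion.

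**Step 4: weight of one subject.** SAP 2.3 reports 97 women randomized 1:1, and 97/2 = 48.5 per arm. The number dosed per arm is not given, so assume 45 to 49.
- 1/45 = 2.22%
- 1/48 = 2.08%
- 1/49 = 2.04%
- Both arms pooled: 1/97 = 1.03%

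The common-AE table in SAP 8.2.3.3 uses a threshold above 2%. Read per arm, one subject can decide whether a term appears. Read across both arms, one subject alone (1.03%) does not reach it.

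**The case against.** There are four serious counter-arguments.

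1. *Nothing in the SAP excludes undated AEs.* This is right. A reader might infer that such events drop out of every AE table by rule, but exclusion is a consequence of literal reading. The permissive bullet also points the other way, and an undated neonatal event evidently did begin after the mother's first dose. What survives is that the SAP gives no default and two of its statements conflict.

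2. *The AE form is not confined to the period after first dose.* Also right. A reader might infer from the opening of Protocol 6.3.8 that every undated AE must be post-dose. The consent-period rule for related SAEs, AE monitoring from Screening and the SAP's pre-treatment state rule that out for mothers and fetuses.

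3. *The affected set may be close to empty.* This is plausible. The SAP describes partial AE dates on the form as month and year with the day missing, partial dates are flagged to data management, the database is cleaned before freeze, and SAEs are reported within 24 hours. Nothing in the documents shows that deliveries elsewhere yield AEs without even a year. Nor is 2% an effect estimate: subjects count once per row, so an undated event matters only if the subject has no other qualifying event there. The rule treats both arms alike, and no between-arm bias is shown.

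4. *Calling every undated event on-treatment would contradict the SAP.* This is correct. The maternal row of 11.6.2.2 moves events possible only during or after labor or delivery, such as postpartum hemorrhage, to the delivery date. Under 11.3.3, on-treatment status ends one day after the treatment stop date. A blanket on-treatment label could therefore misplace an event occurring weeks later, so the default has to follow the existing rows.

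**Conclusion.** The point holds as a gap and an internal conflict. Under SAP 11.6.2.2, 8.2.3 and 11.3.3 taken together, an AE with a wholly missing start date has no defined route into the AE, SAE, AESI or DRE tables. The permissive bullet does not repair this, because it presupposes a status that cannot be derived without the date. For neonatal events, leaving them out would have no timing rationale.

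The importance is minor. The number of undated AEs is unknown and probably small, and the listings keep them visible. The per-arm weight of 2.04% to 2.22% rests on the assumed 45 to 49 dosed and describes one subject only. The documents do not support a claim that safety results are materially distorted.

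**What to change.** Reconcile the two bullets in the general AE row of SAP 11.6.2.2 and state one default:

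- An AE with a wholly missing start date is counted as starting on or after first study treatment, unless its end date or other data show that it preceded first dose.
- Neonatal events are always counted, with the birth date as start, in line with the neonatal row.
- Maternal events possible only during or after labor or delivery take the delivery date, in line with the maternal row.
- Other maternal and fetal events take the first treatment date and are on-treatment, the worst case already used for partial dates.
- Listings keep the date blank.

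The cost is a few lines of SAP text and derivation code. The medical-monitor identification of delivery-only events, which the maternal row already requires, would extend to undated ones. The downside is that an occasional pre-dose event may be counted, or a later event labelled on-treatment. SAP 1 requires analysis decisions before database freeze and unblinding, so the default should be fixed by then.

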11.7.1. Time to Delivery

The time to delivery is defined as the days between the delivery and start time of the infusion of IP. If the delivery date is missing or unknown i.e. subjects withdrew from the study or lost to follow-up, the time to delivery data will be the missing data, which will be handled in below methods.

This analysis addresses the question “What is the prolongation effect for the mother of an initial decision to prescribe treatment, regardless of what subjects received?” This is also referred to as a *de facto* analysis (Carpenter 2013). The treatment effect on the time to delivery will be estimated on randomized subjects regardless of adherence. The delivery data after treatment discontinuation, treatment switch (i.e. at retreatment), or use of rescue medication will be collected and will be included in the primary analysis. Missing data from subjects who withdraw from study participation will be imputed using last contact date or last record available in the study database. The last record are those clinical records that the subjects were last contacted but remained undelivered. For those subjects who are lost to follow-up, a date of birth of delivery date will be obtained from the search of national database if applicable.

